future research studies. (2) To minimize the risk of distress arising from the assessment procedure, study staff that has been adequately trained in the assessment battery will complete all assessments, and [the PIs] will supervise all assessors. (3) To minimize risks due to tDCS, all participants will be carefully screened prior to tDCS for contraindications to tDCS. Moreover, we will obtain a release to gather information from participants' current medical providers for screening purposes and ongoing clinical record keeping. All tDCS will be administered by a trained member of the research staff under the supervision of a credentialed physician (Dr. [Name] or covering physician). Use of an electrically isolated power source (i.e., battery-powered DC stimulation device) also protects against delivery of more intense currents than intended. Participants will be closely observed for signs of skin burns, discomfort, or other stress. Participants will be closely monitored to ensure the electrode sponges stay moist with saline in order to help prevent burns by improving electrode-to-skin contact. Participants will have the option of discontinuing the study at any time and will be explicitly instructed to inform the experimenters immediately if they experience any discomfort. The experimenter will inform the supervising physician about any participant who has significant skin discomfort or a skin lesion after current delivery. If there is any doubt about the mental or physical status of an individual after testing, the PI or other supervising physician will evaluate the participants and make a recommendation for follow-up care, if required. Telephone or in-person follow-up will be arranged as needed and will not be considered a protocol deviation. Adverse effects will be monitored regularly using the SAFTEE-SI. This measure includes symptoms of hypomania, including feeling hyper, unable to sit still, changes in appetite, and sleep disturbance, as well as a number of frequently reported side effects in clinical trials. Any participant judged on clinical grounds to have suffered adverse effects will thus be evaluated and treated as necessary and withdrawn from the study, if necessary. For each SAFTEE item, participants are asked to report how bothersome each symptom on the form has been for him/her in the past week, with response options "None," "Mild," "Moderate," or "Severe." Additionally, a single item inquires about how much all reported side-effects have bothered the participant or interfered with daily activities (response options: "No side effects," "Mildly," "Moderately," or "Markedly"). The SAFTEE-SI will be administered at baseline, once per week during the 5.5 week protocol, at post-treatment, and at 1 month follow-up. At each administration, the evaluator will note items rated more bothersome than during the previous administration and will inquire further about each such item. The therapist or evaluator will also inquire in an open-ended fashion about any other adverse effects experienced which are not listed on the SAFTEE-SI and will document the nature and tolerability of any additional side-effects reported. For any item rated "severe," or if the participant reports that side effects are interfering with daily activities "markedly," the therapist or evaluator will notify Dr. [Name] MD (PI) (or covering physician) immediately. Dr. [Name] (or covering physician) will provide further evaluation as medically necessary and we will take appropriate safety measures such as study withdrawal and/or referral to higher level of clinical care, if necessary. Any item rated as "moderate" or "moderately" interfering will be reported to Dr. [Name] by the therapist or evaluator within 24 hours. All other reported side-effects endorsed on the SAFTEE-SI will be discussed with Dr. [Name] during weekly meetings of study staff. Follow-up or further evaluation will occur as medically necessary. (4) To minimize the risk of distress due to treatment procedures, we have selected a treatment which has been shown to be efficacious in reducing OCD symptoms. While this treatment involves clients placing themselves in situations which provoke anxiety, this is necessary and effective for clinical improvement and generally represents no more distress than is experienced in daily living for these individuals. Participants will be informed that they will be encouraged to

Date most recently revised (02/16/18)

tolerate the discomfort during the sessions but that they can stop the exercises at any time. In the case of a participant who experiences extreme distress, clinical judgment and consultation will be used to determine whether the participant should be discontinued from the study. Participants who experience a significant worsening of symptoms during the study will be discontinued and referred for alternative treatment.

To minimize risk of clinical deterioration, we have excluded participants from entry into the study who have active suicidal or homicidal ideation. At baseline, participants will be provided with a set of emergency contact numbers, including phone numbers for local mental health care providers ([Hospital Names]). One of the PIs or a covering clinician will also be available at all times to study participants in the event of a clinical emergency. All participants will be given oral and written information on how to reach the PIs in the case of such an emergency; participants will be told to contact research personnel by telephone or pager for any significant worsening of symptoms or adverse events, and may be seen for an additional evaluation, which will not be considered a protocol violation. We will assess suicide risk at baseline and every week using item 9 on the BDI-II to screen for suicidal ideation. Any presence (BDI-II item 9 > 0) or increase in suicidal ideation will result in a clinical assessment for suicide risk by the clinician and clinically appropriate steps will be taken (e.g., creating a plan for safety or higher level of clinical care, if necessary). We will monitor clinical symptoms weekly using the BDI, BAI, and Y-BOCS. In the event that a participant experiences significant symptom worsening (i.e., 25% increase of pre-randomization Y-BOCS), he or she will be more thoroughly evaluated and we will take appropriate safety measures such as study withdrawal or a higher level of clinical care, if necessary. Participants will be offered referrals to alternative treatment at study discontinuation.

D.2. Measures to ensure confidentiality

(2) To protect against breaches of confidentiality, all information collected from participants will be handled by staff trained in the responsible conduct of research who have passed ethics training via the CITI Course for the Protection of Human Subjects or the NIH Human Participants Protection Education for Research Teams training. Audio recordings of sessions will be immediately uploaded onto a secure research server and deleted from the audio recording device – these recordings will be identified by code number only. All study forms and data will be identified only by code numbers, and will be stored in locked file cabinets or on secure research servers. Identifying information (contact information, name, consent documents) will be separated from the research data and be stored separately in a different locked file cabinet. REDCap (Research Electronic Data Capture) will be used for data collection, entry and management. REDCap, maintained by [Hospital] Data Center, is a secure, web application designed to support data capture for research studies, providing user-friendly web-based case report forms, real-time data entry validation (e.g. for data types and range checks), audit trails and a de-identified data export mechanism to common statistical packages (SPSS, SAS, Stata, R/S-Plus). All data collected and entered into REDCap will be identified only by patient ID; No PHI will be stored in REDCap. All other computerized data, including digital audio files of assessments and treatment sessions, will be stored on a secure drive, password-protected, and will be accessible only to research staff. These files will be transferred to the secure drive immediately following assessments and treatment sessions and deleted from the digital recording device. Digital audio files will be labeled only with subject ID number. Digital audio files will be erased at the end of

this study. No personal participant information will be presented in any publication or presentations resulting from this research.

D.3. Data safety monitoring plan

Procedures to protect participant confidentiality are described above (section D.2.). [The PIs] will be responsible for supervision of data entry and management and training of study personnel. Hard copy data will be stored in a filing cabinet in one of the PI's locked offices. Digital audio files will be stored on a secure server, and labeled only with participant unique identification code. In order to maintain anonymity in computer data files participants will be only listed with their unique identification code. The PI's will monitor procedures for assuring participant privacy and confidentiality, and the quality and integrity of data collected. Corrective action will be taken as needed. Should any adverse events arise, the PI's will be responsible for completing an Adverse Events Form and reporting Serious Adverse Events to the [Hospital Name] IRB within 24 hours of having received notice of the event. The PI will gather any information needed to investigate the event and to determine subsequent action. Any subsequent action will be documented and reported to the [Hospital Name] IRB.

This study has also appointed a data safety monitoring board (DSMB). Members of the DSMB include [Name] (who will serve as DSMB Chair), [Name], and [Name]. Dr. [Name], of [Affiliation], has expertise in behavior therapy for OCD and statistics. Dr. [Name], of the [Affiliation], has expertise in OCD, neuromodulation, and clinical trials. Dr. [Name] has expertise in clinical bioethics, with a focus on neuroethics. This board convenes twice per year (unless more frequent meetings are deemed necessary) and is responsible for reviewing the research protocol and plans for data and safety monitoring, evaluating the progress of the trial, and inquiring for further information as necessary to accomplish their mission, and maintaining confidentiality during all phases of the trial including the monitoring, preparation of interim results, review and response to monitoring recommendation. As they deem necessary, the members of the DSMB will evaluate whether the presence of side effects or adverse consequences are significant enough to warrant amendment, suspension, or early termination of the study and will independently make recommendations to the PI to continue, to amend or to terminate the trial.

E. Potential Benefits

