Enhancing inhibitory control via non-invasive neurostimulation may improve the efficacy and efficiency of ERP for OCD. The right inferior frontal gyrus (rIFG) is a particularly promising target for such an approach. This region is a key node in neurocircuitry underlying inhibition of a prepotent response. The location of rIFG makes it easily accessible to tDCS, a type of non-invasive neurostimulation delivering a weak electrical current (1-2 mA) via two electrodes placed on the scalp. Neurostimulation via tDCS modulates neuronal excitability by changing membrane potentials and can enhance behavioral plasticity. In healthy individuals, tDCS over rIFG improves inhibitory control of a prepotent response during the SST, a well-established response inhibition paradigm. Such effects have been seen after a single tDCS session, and when stimulation over rIFG was delivered during a course of inhibition training sessions over four days. We propose to extend this approach by coupling tDCS and behavioral training, i.e., ERP, to inhibit compulsive behaviors in OCD.

C. Experimental Method

1. Brief Description of Subjects

For the TIES (Therapy Integrating Exposure and Stimulation) study we will recruit 32 patients with a primary diagnosis of OCD, aged 18-65, with clinically significant OCD symptoms (Y-BOCS total score of ≥ 16). Participants will be naïve to tDCS and will never have completed a minimally adequate trial of ERP (see human subjects section below for additional inclusion/exclusion criteria).

2. Study Design

For this study we will recruit 32 patients with a primary diagnosis of OCD. Each participant will undergo an assessment which will include a structured clinical interview, brief assessments of depression, anxiety, OCD symptoms, and medication and treatment history. Participants will be randomized to one of two combination interventions: Exposure and response prevention (ERP) plus active transcranial direct current stimulation (tDCS) over right inferior frontal gyrus (rIFG) or ERP plus sham tDCS over rIFG. Each group will complete 1 session of psychoeducation and treatment planning, followed by 10 90-minute sessions of their assigned combination intervention. Participants will also complete a post-treatment and one month follow-up assessment.

3. Specific Procedures or Treatments

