Assessment Training and Monitoring of Treatment Integrity. Assessments will be completed by a trained, supervised, advanced (i.e., BA or higher) evaluator who will be kept blind to participant’s group assignment. The evaluator will initially be trained to an inter-rater reliability of ≥ 0.80 . Assessments will be audio recorded and will be checked periodically to minimize rater drift. To Date most recently revised (02/16/18)

ensure fidelity to the intervention and consistency between therapists, study therapists will undergo training in this approach including directed readings and regular supervision of on-going cases. Treatment sessions will be audio recorded and a randomly selected 15% of sessions will be reviewed to ensure adherence to the treatment protocol.

Participant Withdrawal. Participants may be withdrawn from the study for any of the following reasons: 1) A significantly deteriorating clinical course, such as the emergence of active suicidal ideation or a need for hospitalization, 2) Significant adverse reaction to tDCS, assessed using a modified version of the Systematic Assessment for Treatment Emergent Events (SAFTEE), 3) Serious physical illness, 4) Missing two consecutive study visits, 5) Initiation or reinstitution of other treatment (psychosocial treatment with proven efficacy, psychotropic medication changes) during the acute treatment phase, 6) Investigators' decision that withdrawal from the study is in the participant's best interest, 7) Participant's decision to withdraw. Reasons for withdrawal will be documented, participants will be referred for appropriate treatment, and we will make every attempt to conduct scheduled follow-ups with those who withdraw. The current study will employ several measures to minimize attrition, including frequent contact with participants for the duration of the study and compensation for participants' time for post-treatment and follow-up assessment visits.

4. Data Analysis

Original Data Analysis Plan:

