Preliminary and Primary Data Analyses. As the proposed study is a small-sample pilot study, our primary focus will be on examining feasibility, acceptability, and direction of effects. Additionally, all randomized participants will be used in an intent-to-treat analysis. We will use chi-square and t-tests to evaluate any differences between the two conditions at baseline on demographic and other relevant variables, such as initial symptom severity, comorbid depression, or patient adherence to ERP homework. If significant differences exist, we will covary for these variables in our analyses (though we do not anticipate significant group differences at baseline, as urn randomization tends to result in balanced samples.)

Aim 1: Establish feasibility and acceptability of research procedures and clinical intervention.

Hypothesis: Patients with OCD will tolerate this combined ERP + tDCS treatment and will find it acceptable, as determined by rates of retention, treatment completion, and patient report. For Aim 1, we will use chi-square or t-test to compare treatment conditions on rates of retention, session attendance, homework and treatment completion, and patient satisfaction on the CSQ-8.

Aim 2: Gather evidence on preliminary efficacy of tDCS over rIFG as an adjunct to ERP for OCD.

Hypothesis: Patients in the group receiving ERP + active tDCS will show greater reduction in symptom severity over 10 sessions of the combined treatment than those receiving ERP + sham tDCS. For Aim 2, we will use repeated-measures ANOVA with a between-group factor (condition) to evaluate differences in Y-BOCS severity between groups across assessment timepoints. Since this is a small pilot study (N=32), we will also examine group means and direction of effects across all timepoints, not relying solely on statistical approaches which may be underpowered to detect a significant effect.

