Aim 3: Characterize the relationship between measures of inhibitory control and outcome of the combined intervention. Hypotheses: a) Response inhibition, as measured by the SST, will improve more after ERP plus active vs sham tDCS; b) Improvement in OCD severity will correspond to improved inhibitory control on the SST; and c) Patients receiving ERP plus active tDCS will report less difficulty inhibiting compulsions during ERP exercises than those receiving ERP plus sham tDCS. To test our hypotheses for Aim 3, we will: a) use independent measures t-tests to compare change in SSRT from pre- to post-treatment between conditions, and from pre-treatment to follow-up; b) compute a correlation between percent change in Y-BOCS score and percent change in SSRT from baseline to post-treatment, and from baseline to 1-month follow-up, c) use an independent measures t-test to compare self-reported mean difficulty inhibiting compulsions (VAS) during ERP across stimulation conditions.

Revised Data Analysis Plan:

Preliminary and Primary Data Analyses. Given that this study resulted in a smaller than anticipated final sample size, we created a revised analysis plan, appropriate for the smaller sample. Consistent with the original plan for this pilot study, our primary focus will be on examining feasibility, acceptability, and direction of effects. Additionally, all randomized participants will be used in an intent-to-treat analysis. Analyses will focus on descriptive statistics (e.g., means or proportions) with between-group effect sizes calculated, as appropriate.

Aim 1: Establish feasibility and acceptability of research procedures and clinical intervention.

Hypothesis: Patients with OCD will tolerate this combined ERP + tDCS treatment and will find it acceptable, as determined by rates of retention, treatment completion, and patient report. Our primary feasibility outcome of interest is rates of session completion. Our primary acceptability outcome is patient-reported client satisfaction.

Aim 2: Gather evidence on preliminary efficacy of tDCS over rIFG as an adjunct to ERP for OCD.

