Hypothesis: Patients in the group receiving ERP + active tDCS will show greater reduction in symptom severity over 10 sessions of the combined treatment than those receiving ERP + sham tDCS. For Aim 2, we will examine group means on the Y-BOCS and direction of effects at post-treatment, and 1-month follow-up, not relying on statistical approaches which will be underpowered to detect an effect. The Y-BOCS is our primary clinical outcome.

Aim 3: Characterize the relationship between measures of inhibitory control and outcome of the combined intervention. Hypotheses: a) Response inhibition, as measured by the SST, will improve more after ERP plus active vs sham tDCS; b) Improvement in OCD severity will correspond to improved inhibitory control on the SST; and c) Patients receiving ERP plus active tDCS will report less difficulty inhibiting compulsions during ERP exercises than those receiving ERP plus sham tDCS. We regard aim 3 and related hypotheses to be largely exploratory. To investigate our hypotheses for Aim 3, we will: a) calculate mean change in SSRT from pre- to post-treatment, and from pre-treatment to follow-up for both conditions, and between groups effect size; b) compute a correlation between percent change in Y-BOCS score and percent change in SSRT from baseline to post-treatment, and from baseline to 1-month follow-up, c) calculate self-reported mean difficulty inhibiting compulsions (VAS) during ERP and direction of effects across stimulation conditions.

D. Material Inducements

Compensation for participation in assessments will be offered as part of this study. No compensation will be offered for participation in ERP sessions. Participants will receive a payment of \$25 for completing the screening assessment. Participants will participate in a total of 8 additional assessments during the study (baseline, sessions 1, 3, 5, 7, 9, post-treatment, and 1 month follow-up); they will receive payment for completion of each of these assessments (\$30 for the baseline assessment, \$10 for each mid-treatment assessments, \$40 for the baseline assessment, and \$40 for the post-treatment assessment) for maximum compensation of \$185 for completing the screening and all assessments. Participants will have the option to receive payment by check in the mail or Stop & Shop gift card after each assessment.

E. Training of Research Personnel

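### The revised plan, written once the final sample size was known, narrows the Y-BOCS reading to two visits and replaces the planned arm tests with descriptive contrasts that need carry no intervals

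*Combined protocol and SAP*

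**What the plan says.** Section II.C.4 (Data Analysis) prints two plans one after the other.

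The Original Data Analysis Plan compares the arms formally under each aim. The Aim 2 text reads: "we will use repeated-measures ANOVA with a between-group factor (condition) to evaluate differences in Y-BOCS severity between groups across assessment timepoints". It then adds a descriptive reading: "Since this is a small pilot study (N=32), we will also examine group means and direction of effects across all timepoints". The reason it gives is that the tests might be too weak to stand alone.

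The Revised Data Analysis Plan gives its reason first: "Given that this study resulted in a smaller than anticipated final sample size, we created a revised analysis plan, appropriate for the smaller sample". It keeps intent-to-treat and the same overall emphasis, "our primary focus will be on examining feasibility, acceptability, and direction of effects". It moves to descriptive statistics, with effect sizes between arms where suitable. For Aim 2 it reads the Y-BOCS means and their direction at post-treatment and at 1 month only, "not relying on statistical approaches which will be underpowered to detect an effect". It names session completion, client satisfaction and the Y-BOCS as the primary feasibility, acceptability and clinical outcomes, and it describes Aim 3 as largely exploratory.

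**The concern.** An analysis plan rewritten at the end of a trial can be sound, but the reader needs to know what changed, why, and what its authors had seen. Here the reason given is the smaller sample and its low power. That reason covers the loss of the tests. It does not cover shortening a descriptive summary that needed no power in the first place.

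The stakes are those of a pilot whose Aim 2 evidence is now means and their direction. If the in-treatment Y-BOCS readings are left out and no interval is shown, a chance difference at two visits can look like a promising signal. The reader would see neither its uncertainty nor the course over treatment that the hypothesis is about.

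**Working it through.** **1. The two plans side by side (II.C.4).**

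- Aim 1. Original: chi-square or t-test between arms on five measures (retention, session attendance, homework completion, treatment completion, CSQ-8). Revised: no test. Session completion and satisfaction are named primary. Retention and treatment completion remain in the hypothesis wording. Homework completion is not mentioned.
- Aim 2. Original: one repeated-measures ANOVA, plus means and direction at all timepoints. Revised: means and direction at two visits, with no effect size named in that paragraph.
- Aim 3a. Original: two t-tests on SSRT change (to post-treatment and to follow-up). Revised: mean changes by arm and an effect size between arms.
- Aim 3b. Correlations over two intervals, unchanged.
- Aim 3c. Original: one t-test on the VAS. Revised: means and direction by arm.

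Between-arm tests removed: 5 + 1 + 2 + 1 = 9. The baseline tests, with their rule for covariate adjustment, are also gone. No interval is required anywhere in the revised plan.

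**2. How far the Y-BOCS reading narrows.** The Monitoring Assessments text has the Y-BOCS at baseline, about weekly in treatment, at post-treatment and at 1 month. Section II.D lists eight assessments after screening: baseline, sessions 1, 3, 5, 7 and 9, post-treatment and 1 month. On that schedule, which is the smaller count if Table 1 marks more sessions, five in-treatment readings drop out: 8 − 1 (baseline) − 2 (kept) = 5. The Aim 2 hypothesis, about reduction across the ten combined sessions, is the same in both plans.

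**3. How much selection the new primary labels involve.** The Y-BOCS was already the only Aim 2 measure and the CSQ-8 the only satisfaction measure. Session completion is the one real choice. The original plan listed four feasibility measures without ranking them, and session completion is closest to attendance.

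**4. Is the low-power reason sound?** The documents give no alpha, power, effect size, SD, allocation ratio or final N, so N=32 cannot be reproduced. Assume 1:1 allocation (n per arm), two-sided alpha 0.05, and a total N from 32 down to 10. Power of a two-sample t-test (noncentral t):

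- N=32: 28% at d=0.5; 59% at d=0.8
- N=20: 18%; 40%
- N=10: 10%; 20%

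So the tests were weak at the planned size and weaker below it. The reason is sound as far as the tests go.

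**5. What description without intervals hides.** The large-sample 95% half-width for a standardised difference d is 1.96 × √(2/n + d²/(4n)). At d=0.5:

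- n=16: 1.96 × √(0.125 + 0.0039) = 0.70
- n=10: 1.96 × √(0.2 + 0.00625) = 0.89
- n=5: 1.96 × √(0.4 + 0.0125) = 1.26

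The chance that the observed direction at one visit is wrong when the true d is 0.5 is Φ(−0.5 × √(n/2)):

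- n=16: Φ(−1.41) = 0.08
- n=10: Φ(−1.12) = 0.13
- n=5: Φ(−0.79) = 0.22

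**The case against.** The case for the revised plan is substantial, and most of it stands.

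- Moving a small pilot to description is defensible. The original plan said its tests might be underpowered at 32; the revised plan says they will be at fewer. Step 4 agrees.
- Arm contrasts survive in another form: effect sizes in general, Y-BOCS means and direction, an SSRT effect size, and VAS direction.
- Post-treatment and 1 month are not new choices. The original Aim 3b already used Y-BOCS change to those two visits. Fixing two visits also leaves less room to choose a favourable one than reading direction at every visit.
- Two of the three primary labels involve no selection among measures, and SSRT was already called the primary variable for inhibitory control under Measures of Inhibitory Control.

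A reader might infer that a report could not separate planned read-outs from later ones, or that the arm comparisons have been abandoned. The documents support neither. Both plans are printed in full under separate headings, so each item can be traced, and the contrasts are replaced rather than removed. A reader might also infer that visits or labels were picked after looking at results. Nothing in the documents shows that; they are silent on who had seen what.

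The objection does not reach three things. No reason is given for dropping the in-treatment Y-BOCS readings from a descriptive summary. Effect sizes are left to judgement, with no intervals. And the revision does not state its date, the final N or its authors' access to data by arm. Evaluators are blinded, but nothing is said about those who revised the plan.

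**Conclusion.** The concern holds in a limited form. After the final sample size was known, the plan replaced nine between-arm tests with descriptive contrasts that need carry no interval, stopped naming homework completion as an arm comparison, and selected session completion as primary for feasibility. It also reduced the Y-BOCS reading to two visits, leaving out five in-treatment readings on the Section II.D schedule. The stated reason justifies dropping the tests but not narrowing the summary.

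The size is moderate. Under the assumed inputs (1:1 allocation, d=0.5, total N from 10 to 32), direction at one visit misleads in 8% to 22% of trials, and an interval would span about ±0.70 to ±1.26 SD. These figures describe the imprecision that the revised presentation leaves unseen. They do not measure bias from the revision, for which the documents offer no evidence. The missing date, final N and access statement would alone be only missing detail. They matter here because they accompany a narrowing with no stated reason.

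**What to change.** Keep the revised summaries and do not bring back the significance tests. Beside them, report each originally specified comparison as an arm difference with a 95% confidence interval:

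- Y-BOCS by arm at every assessment timepoint, including those during treatment
- retention, session attendance, homework completion, treatment completion and CSQ-8
- SSRT change to post-treatment and to follow-up, and mean VAS difficulty

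Label each read-out as original or revised, including the session-completion designation and the two-visit Y-BOCS reading. State the date of the revision, the final N by arm, and whether anyone who revised the plan had seen data by arm.

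The cost is a few more table rows from data already scheduled for collection. The intervals will be wide, which is an honest picture of a pilot this size.
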